Hence, reducing the impact of cognitive impairments in ABI may contribute to improvements in mood alongside BA. Therefore, the proposed study will investigate the feasibility and acceptability of two ABI-specific BA interventions, and whether one or other intervention is superior in improving mood and activity levels and how each compares to participants assessed and re-assessed on the outcome measures over the same period but with no intervention other than care as usual (waitlist condition)

Objectives

The primary objective of the MAPLES study is to determine the feasibility of two Behavioural Activation group interventions in individuals with an acquired brain injury (ABI) with low mood. This will be based on participant retention from baseline to 1-month post-intervention, acceptability of the proposed skills in the group sessions and assessments, and participant feedback from the exit interview. The two behavioural activation groups will be administered both in person and online.

A secondary objective of the MAPLES study is to evaluate whether training adults with an acquired brain injury to plan and engage in meaningful, valued, and/or enjoyable activities has detectable effects on activity level and mood compared to a waitlist control condition.

Hypotheses

There are no specific hypotheses related to the level of acceptability and feasibility of the trial whether in person or online.

Study Groups

- 1) Activity Planning Group – BA Intervention arm
- 2) Activity Engagement Group – the social group
- 3) Waitlist Group

HA-1: Relative to participants in the Waitlist Group, participants in the Activity Planning and Activity Engagement Groups will have greater increases in activity level from pre- to post-intervention and at 1 month post-intervention.

H0-1: There will be no differences in activity level from pre- to post-intervention and at 1 month post-intervention across all groups.

HA-2: Relative to participants in the Waitlist Group, participants in the Activity Planning and Activity Engagement Groups will have greater improvements in mood from pre- to post-intervention and at 1 month post-intervention.

H0-2: There will be no differences in mood from pre- to post-intervention and at 1 month post-intervention across all groups

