The COVID-19 pandemic has meant that we have had to suspend all in-person contact with research participants. In the current substantial amendment, we are proposing to continue the study using only telephone and on-line contact with participants. Whilst this was not part of our original plan, it does

MAPLES Pilot Study for Low Mood in ABI

offer an opportunity to examine the relative feasibility and acceptability of in-person vs. online videoconferencing groups. This is useful both during the pandemic, whilst social distancing restrictions remain in place, and also afterwards when new means of tele-therapy may have value for patients (e.g. those that find it difficult to travel) and services.

STUDY DESIGN and METHODS of DATA COLLECTION AND DATA ANALYSIS

Trial Design

Activity Planning Group

Generally, those receiving BA training develop and maintain a schedule based on activities that have been enjoyable, pleasant, meaningful, or interesting in the past (Mazzuchelli et al., 2010). Clients are then instructed to monitor their daily mood and participation in these activities to identify the connection between them. Clients are then taught how to increase the frequency and quality of positive events and decrease negative ones (Lewinsohn, 1976; Lewinsohn et al., 1980). In GMT, participants learn how to identify precursors to becoming distracted from their goals and strategies to orient themselves to their environment in order to prevent goal neglect (Levine et al., 2000, 2011).

The intervention will consist of weekly 1 hour group sessions over the course of 8 weeks, covering 8 overarching themes:

- 1) Introduction to Group Therapy
- 2) Identifying Enjoyable Activities
- 3) The Automatic Pilot and Planning Pleasurable Activities
- 4) Goal Review and Balancing Enjoyable and Routine Activities
- 5) Identifying Solutions to Goal Neglect
- 6) Increasing Mastery and Managing Fatigue
- 7) Active Approaches to Engagement
- 8) Relapse Prevention

All sessions will be administered by [name]. Although we have received feedback from individuals with an ABI on the content covered within the Activity Planning Group, if participants within the MAPLES study react negatively to the content covered within the program then such content will be removed from the intervention or restructured so as to not potentially cause distress for future participants.

Activity Engagement Group

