Individuals randomised to the Activity Engagement Group will meet weekly for 8 weeks for 1 hour and engage in various social activities such as board games, crafting, puzzles, similar to the social group in McDonald et al.'s (2008) social arm. Participants in this group will not have specific therapeutic goals and outcomes and will only be encouraged within each session to engage in activities within the group. The group will follow the below schedule:

- 1) Board games
- 2) Shirt Making
- 3) Puzzles
- 4) Painting
- 5) Trivia Day/"Pub Quiz"
- 6) Figurine painting
- 7) Origami/papercraft
- 8) Clay sculptures

MAPLES Pilot Study for Low Mood in ABI

All sessions will be administered by [name]. If participants within the Activity Engagement group strongly oppose engaging in one of the above sessions (e.g., clay sculptures) that session will be replaced with a reasonable substitute (e.g., knitting).

The online versions of the two groups will resemble the in-person groups as closely as possible. Participants will be invited to take part using video-conferencing software. Our plan at the outset is to use GoToMeeting video-conferencing software because it is easy to use, has a number of good security features and does not require participants to sign up for an account. It has also been recommended by our co-sponsor, Cambridge University Hospitals NHS Trust. We will continue to review developments in this area and may switch to an alternative service if there are advantages for data security and ease of use.

In line with the nature of the online groups and restrictions imposed by the COVID-19 crisis, the following changes will be implemented: The Activity Planning Group will focus on activities that fit with current health advice (e.g. that can take place in the home, that do not involve face-to-face contact with others, that fit with current outside home/exercise advice). The Activity Engagement group will focus on verbal games, quizzes and general conversation rather than crafts.

Waitlist Group

Individuals who are randomised to this arm of the trial will be waitlisted for 8 weeks, and then randomised again into either the Activity Planning Group or Activity Engagement Group.

Method

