All participants will complete a baseline assessment, a post-intervention assessment, and a 1-month follow-up assessment. Participants in the waitlist group will complete an additional baseline assessment prior to being re-randomised into either the Activity Planning Group or the Activity Engagement.

Randomisation Procedure

The MAPLES study will use pre-determined randomisation. Prior to any recruitment, [name] (Departmental Statistician) will generate a randomisation sequence known only to him in which the condition allocation of each consecutive consenting participant will be listed. These will be placed in sealed envelopes showing only the participant number. After conducting a baseline assessment, the researcher ([name]) will simply open the next envelope in the sequence. In order to maintain approximate parity in group size across the duration of the study (e.g. such that participants recruited later are not more likely to appear in one or other condition and such that the groups are approximately balanced at any point of study termination) randomisation will occur in subblocks of varying lengths. The researcher will not know the length of the current block over which randomisation has been balanced such that she could guess that, e.g. if the last 3 allocations had been to condition A, the next was bound to be B. At the outset of the study, [name] will similarly create randomised sequence that will determine to which of the two intervention groups each participant initially randomised to the wait-list condition will be allocated after the wait period. Again, these will be balanced over variable length subblocks and will be opened in order by the researcher after completing the second baseline assessment with Waitlist participants. In this manner, randomisation is conducted blind to any information about the participants and cannot influence or be influenced by the results of baseline assessments.

Baseline and Outcome Measures.

Demographic information will be collected from participants, including months since injury, type and cause of injury (e.g., non-TBI, hypoxia), comorbidities, Glasgow Coma Scale Scores, length of post-

MAPLES Pilot Study for Low Mood in ABI

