The groups in this trial are being offered in addition to any services normally accessed by participants. The study will not therefore deprive participants of other interventions and, potentially, of course, offers something beneficial to which they might not otherwise have access. It is possible that being offered the prospect of a therapeutic group but then having to wait some weeks before it begins would induce distress at the delay that would not otherwise have occurred. Such delays are, of course, common in clinical services and would be inevitable given the study's resources, access to rooms, need to recruit certain numbers for a group to begin etc. – it would be very rare to go straight from referral/initial assessment straight into such an intervention. We are also at pains to point out to potential participants that the reason this is research is because we do not know whether one or other intervention is of any benefit and the occurrence of delay is an important aspect of drawing meaningful scientific inference.

Participants who choose to have their contact details retained for receiving a summary of the study results and/or details about other research studies will only have their information stored on the MRC CBU secure "haven" and paper copies of contact details will be shredded after transferring details to the CBU computer server. Upon each contact beyond the MAPLES study, participants will have the option to have their contact details permanently deleted from the MRC CBU servers and not be contacted again.

Research Ethics Committee (REC) and other Regulatory review & reports

Prior to any data collection, a favourable opinion will be sought from the Cambridge Central Research Ethics Committee (REC). A detailed record will be kept of all correspondence with the REC, and annual reports will be submitted as required. Upon completion of the study, the REC will be notified immediately. The REC will additionally be notified in the case of premature termination of the trial and in the case of adverse events.

Regulatory Review & Compliance

Prior to recruitment, [name] and the research team will ensure that appropriate approvals are in place. For any amendment, the research team will in agreement with the sponsor will submit information to the appropriate REC following the appropriate timeframe.

Peer review

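### The plan does not secure equal baseline-to-reassessment intervals: the active arms' interval is 8 weeks plus any wait for a group to start, the Waitlist's is 8 weeks

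*Combined protocol and SAP*

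**What the plan says.** The last paragraph of Background and Rationale, just before Objectives, describes the Waitlist as participants "assessed and re-assessed on the outcome measures over the same period but with no intervention other than care as usual". HA-1 and HA-2 then compare change from before to after the intervention between the two active arms and the Waitlist.

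The timing has to be assembled from several sections:

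- **Randomisation Procedure.** Allocation is individual and sequential: "the condition allocation of each consecutive consenting participant will be listed". Once a participant's baseline is done, the researcher "will simply open the next envelope in the sequence".
- **Activity Planning Group.** The intervention is "weekly 1 hour group sessions over the course of 8 weeks". The Activity Engagement Group has the same number, length and frequency of sessions.
- **Waitlist Group and Method.** Waitlist participants "will be waitlisted for 8 weeks" and complete an additional baseline before being re-randomised.
- **Baseline and Outcome Measures.** The battery is given at Time 1 (baseline), Time 2 (post-intervention) and Time 3 (one month later). Only Waitlist participants repeat it before starting a group.
- **Assessment and management of risk.** Delay before a group is described as unavoidable, one reason being the "need to recruit certain numbers for a group to begin".
- **Analysis.** A general linear model uses the BADS across assessment points. Elapsed time is not mentioned.

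**The concern.** A waitlist control removes natural change only if the untreated arm is observed for as long as the treated arms. Here the active arms' clock starts at an individual baseline and stops after the eighth session of a group that may begin some time later. The Waitlist clock is set at 8 weeks. Any wait between baseline and first session lengthens the interval in the active arms alone.

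Entry is allowed from 3 months after injury, participants are selected for low mood, and part of the study runs under changing pandemic restrictions, so untreated change over some weeks is plausible. Whatever change accrues during the extra weeks is credited to the interventions. The plan intends to estimate effect sizes from these data and refers to a later full-scale trial, so a timing artefact could be carried forward.

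**Working it through.** The plan states no figure for the interval, group size, recruitment rate or sample size, so there is nothing to reproduce.

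**Step 1: interval arithmetic, from the documents.** Let w be the weeks from Time 1 to the first session.

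- Active arms, Time 1 to Time 2: w + 8 weeks.
- Waitlist, first to second baseline: 8 weeks.
- Difference: w weeks.

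The intervals agree only if w = 0. For w = 2, 4 and 8 the active interval is 10, 12 and 16 weeks against 8, ratios of 1.25, 1.5 and 2.0. No section caps w, schedules baselines around a group start, or ties the Waitlist reassessment to a concurrent group.

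**Step 2: how large w might be, on assumed values.** Suppose r recruits a month are allocated 1:1:1 and a group starts when g people have been allocated to it. If only initial allocations fill groups, the mean wait in weeks is

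(g − 1)/2 × 3/r × 52/12.

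- g = 4, r = 8: 1.5 × 0.375 × 4.333 = 2.4 weeks.
- g = 6, r = 4: 2.5 × 0.75 × 4.333 = 8.1 weeks.

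Re-randomised Waitlist participants would also fill groups. Simulating that over the same range (4 to 8 recruits a month, groups of 4 to 6) gives mean waits of about 1.7 to 5.6 weeks. Across both cases the active interval is about 9.7 to 16.1 weeks. Slower recruitment or larger groups lengthen it: at 3 a month and groups of 8, the simulated mean wait is 10.2 weeks.

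**Step 3: effect on the contrast, on assumed drift.** Spurious difference = drift per week × w. With untreated change of 0.01 to 0.03 SD a week (not in the documents):

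- lower end: 0.01 × 1.7 = 0.02 SD;
- upper end: 0.03 × 8.1 = 0.24 SD.

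The slow-recruitment case would give 0.03 × 10.2 = 0.31 SD. The sign follows the sign of the drift.

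**Step 4: whether adjustment could help.** Within an active group, early joiners wait longest and the last joiner hardly waits, so elapsed time varies inside the active arms. A simulation assumed 60 recruits, 4 a month, groups of 6, Waitlist participants joining later groups, linear drift of 0.03 SD a week and a true effect of 0.40 SD:

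| Model | Mean estimate | SE |
|---|---|---|
| Without elapsed time | 0.59 | 0.27 |
| With elapsed time | about 0.40 | 0.35 |

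Adjustment removes nearly all the bias under linear drift, at a clear cost in precision.

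**The case against.** The strongest reply is that the documents leave a detail open and do not contradict themselves. They say a baseline is scheduled after contact or screening, but not when. The team could pool eligible people, assess them over a week or two before a planned start, and open each envelope straight after each baseline. The intervals would then nearly match. This stands to the extent that a reader might infer that matching is impossible unless envelopes are held back, and the documents do not support that. They neither describe nor exclude pooling. What remains is that equal intervals are asserted and nothing in the schedule delivers them.

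Second, the risk section's remark that "it would be very rare to go straight from referral/initial assessment straight into such an intervention" might be read as an admission of a gap after Time 1. The passage justifies delay on ethical grounds and does not schedule the active arms. Elsewhere the protocol uses the term initial assessment for an assessment at the NHS service, and calls the trial visit the baseline assessment. The remark may therefore concern time before Time 1, and the point does not rest on it. The need to gather numbers applies to any group, though the text does not say on which side of baseline that wait falls.

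Third, a reader might infer that adjustment is useless because elapsed time is confounded with arm. Step 4 shows otherwise, given linear drift.

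Fourth, this is a pilot whose primary objective is feasibility, and even 0.24 SD is below the SE of 0.27 in the assumed 60-person example. That limits the consequence. It does not justify leaving an avoidable systematic difference in place.

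**Conclusion.** The point holds as a gap between the stated comparison and the schedule. As written, the plan allows the active arms a longer baseline-to-Time 2 interval than the Waitlist, by the length of any wait after baseline. That part is arithmetic from the protocol.

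The size cannot be derived from the documents. With 4 to 8 recruits a month, groups of 4 to 6 and drift of 0.01 to 0.03 SD a week, all assumed, it ranges from negligible to about 0.2 SD. A reader might infer that the bias must favour the interventions. It does so only if untreated mood and activity improve; if they worsen, for example as pandemic restrictions tighten, it works against them. The exclusion of people on unstable psychotropic medication also limits one source of drift.

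The contrasts affected are active versus Waitlist at Time 2. Planning versus Engagement is affected only if their groups fill at different speeds. The change is worth making because this is the trial's only untreated comparison and the remedy is cheap, but it does not threaten the primary feasibility objective.

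**What to change.** 1. Pool eligible recruits and complete Time 1 for each batch in a short, stated window before a planned group start date. Open each envelope straight after that participant's baseline, as Randomisation Procedure already provides.
2. Where a group still starts late, date the Waitlist second assessment to match Time 2 of the concurrent groups, and reconcile this with the 8 weeks stated under Waitlist Group.
3. Record the dates of baseline, allocation, first session and each later assessment. Report the baseline-to-Time 2 interval by arm.
4. Add a sensitivity analysis with elapsed time in the model, stating that it assumes linear drift and costs precision.

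The cost is protocol wording and scheduling. Much of the wait moves from after baseline to before it, so some people wait between consent and baseline. A batch may not fill both groups exactly, because allocation remains random. Under step 2 some Waitlist participants may wait somewhat longer, which should be weighed against the distress from delay that the risk section already acknowledges.

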Low mood/depression occurs at significantly elevated rate following acquired brain injury (ABI). Unfortunately, we lack a good evidence-base for ameliorative interventions in this group. Cognitive Behavioural Therapy, for example, appears to be less effective following ABI because of the heavy demands it places on memory, mental flexibility, and comprehension. Behavioural Activation (BA), which places much lower demands on these abilities, is a promising alternative. Depression leads to reduced participation in potentially meaningful and/or enjoyable activities – people may have difficulty anticipating positive experiences, avoid situations through fear of negative outcomes, find it hard to plan or initiate activities etc. This situation is likely to be exacerbated after ABI where physical and cognitive problems can present additional barriers. The central tenet of BA, which has established efficacy in reducing depression in the general population, is that this lack of positive reinforcement creates a cycle that perpetuates low mood. Put simply, it aims to reverse this by helping individuals to schedule and engage in activities. Here we seek to examine the feasibility and acceptability of two group approaches to increasing engagement in meaningful activities in adults with an ABI. The first approach will train participants to plan and engage in pleasurable activities *outside* of the group and develop skills to overcome barriers to engagement. This group will explicitly help participants

**MAPLES Pilot Study for Low Mood
in ABI**

understand the link between activity level and mood. The second approach will encourage participants to engage in social activities *within* the group, such as crafts, puzzles, and board games and will not explicitly highlight the link between activity level and mood. Participants will be randomised to either the BA training group, the social group, or to a group of waitlisted individuals. This allows us to create a ‘treatment as usual’ control for the relative efficacy of both groups by repeating the outcome measures before and after this ‘waitlist’ period, before these participants take up their group places.

Study Title	Mood, Activity Participation, and Leisure Engagement Satisfaction (MAPLES): A Pilot Feasibility Study for Low Mood in Acquired Brain Injury.
Internal ref. no. (or short title)	MAPLES Pilot Study for Low Mood in ABI
Study Design	Randomised Controlled Trial

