Here, we will investigate the benefits of BA primarily in people who have sustained traumatic brain injuries (TBI) and, for the first time in ABI, examine the efficacy of group rather than individual therapy. There are clear economic advantages to group, compared with individual, therapy and, when they work well, the supportive dynamics of groups of people with similar challenges can enhance therapeutic effects. It might be expected that conventional BA, in which people learn about the importance of activity engagement, of scheduling activities in everyday life and of overcoming barriers and resisting avoidant behaviour would lead to more generalised and lasting gains than simply engaging in rewarding activities without such knowledge and skill acquisition. However, it is also possible that cognitive problems (e.g. in remembering details) may undermine these gains. Accordingly, we will compare this conventional BA group ("activity planning") with a second intervention group ("activity engagement") in which participants will be encouraged to engage in potentially rewarding activities (crafts, games, social discussion) but which will not emphasise planning and scheduling activities outside of the group. Here it is possible that, through positive experiences of engagement, participants implicitly or explicitly generalise to increase activity levels in daily life. This second intervention also serves to make it clearer, should the "activity planning" be associated with

MAPLES Pilot Study for Low Mood in ABI

greater gains in activity and mood that it is likely attributable to the conventional BA component rather than more general group dynamics.

Cognitive impairments in ABI such as inability to override habits in favour of new behaviours may pose barriers to BA's success. Incorporating cognitive training developed specifically for ABI may enhance the effectiveness of BA. For example, Goal Management Training (GMT; (Levine et al., 2000, 2011) is designed to help individuals with ABI overcome habits, generate solutions, and attain goals. GMT is well-suited to groups, with participants providing support and feedback to one another, alongside "homework" designed to encourage understanding and application of skills (Levine et al., 2011).

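### HA-1, H0-1, HA-2 and H0-2 extend the Waitlist comparison to 1 month post-intervention, where no matching untreated waitlist reading is scheduled

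*Combined protocol and SAP*

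**What the plan says.** The Hypotheses section frames HA-1 and HA-2 as comparisons with the Waitlist Group. Under HA-1 the two intervention groups "will have greater increases in activity level from pre- to post-intervention and at 1 month post-intervention"; under HA-2 they "will have greater improvements in mood from pre- to post-intervention and at 1 month post-intervention". H0-1 reads "There will be no differences in activity level from pre- to post-intervention and at 1 month post-intervention across all groups", and H0-2 does the same for mood.

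The Waitlist Group section says that people in this arm "will be waitlisted for 8 weeks, and then randomised again into either the Activity Planning Group or Activity Engagement Group". The Method section gives every participant a baseline, a post-intervention and a 1-month assessment. It gives the waitlist arm one more, a second baseline before re-randomisation. The schedule paragraph under Neuropsychological Assessment repeats this and ties Times 2 and 3 to the intervention.

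Two places define the control. The opening summary has the outcome measures taken at both ends of the wait, "before these participants take up their group places". Background and Rationale describes people assessed and "re-assessed on the outcome measures over the same period but with no intervention other than care as usual (waitlist condition").

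The Analysis section specifies a general linear model on the BADS over the assessment points. It does not say which waitlist reading is the control value, or how waitlist readings after crossover are coded.

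**The concern.** The hypotheses promise a Waitlist contrast at two time points, but the schedule supplies an untreated waitlist value for only one of them. At 1 month the analyst has two candidates. The second baseline is untreated but was taken too early. The waitlist's own 1-month visit carries the right label but follows active treatment.

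Natural change is plausible in either direction. The inclusion criteria admit people from 3 months after injury with no upper limit, so spontaneous improvement is possible. The study also continued under COVID-19 restrictions, so worsening is possible. A reported 1-month benefit over waitlist could be partly drift, or drift could hide a real one. The Analysis section says that effect sizes will be estimated from the trial data, and the exit interviews are meant to inform a full-scale trial, so a contaminated 1-month estimate could be carried forward.

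**Working it through.** The plan gives no figure to reproduce here; the check is to lay out the assessment calendar.

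**Inputs from the documents.** Both interventions last 8 weeks (Activity Planning Group and Activity Engagement Group sections). The wait is 8 weeks (Waitlist Group). The follow-up is 1 month after the intervention, and the waitlist arm has one extra assessment, before re-randomisation (Method).

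**Assumptions.** On the nominal schedule, groups start promptly after the assessment that precedes them. One month is taken as 4 weeks.

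**Nominal calendar, in weeks from first baseline**

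- Active arms: Time 1 at 0, Time 2 at 8, Time 3 at 8 + 4 = 12.
- Waitlist, untreated: first baseline at 0, second baseline at 8.
- Waitlist, treated: own Time 2 at 8 + 8 = 16, own Time 3 at 16 + 4 = 20.

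At week 12 the waitlist participants are about 4 weeks into their own 8-week group, with no assessment scheduled. The last untreated reading is 12 - 8 = 4 weeks too early. Their own 1-month reading is 20 - 12 = 8 weeks later and follows treatment.

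**Could start delays repair this?** Let d be the weeks from first baseline to first session in the active arms, and w the week of the second baseline. The signed gap in elapsed time (active minus waitlist) is:

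- at Time 2: (d + 8) - w = 8 + d - w
- at Time 3: (d + 12) - w = 12 + d - w

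The two gaps differ by 4 weeks for every d and w, so a single second baseline cannot match both visits. Examples:

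- d = 0, w = 8: gaps 0 and +4.
- d = 0, w = 10: gaps -2 and +2.
- d = 0, w = 12: gaps -4 and 0. Time 3 is now matched, but Time 2 is not.

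**Illustrative size.** Bias = gap x drift per week. The documents give no drift, so a range of -0.03 to +0.03 SD per week is assumed. On the nominal schedule the bias is 0 at Time 2, and 4 x (-0.03 to +0.03) = -0.12 to +0.12 SD at Time 3. With a month of 365.25/12/7 = 4.35 weeks, the range is about -0.13 to +0.13 SD. With a positive gap, natural improvement flatters the active arms and natural worsening counts against them; with a negative gap both reverse.

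**The case against.** The strongest reply is that the plan already identifies its control. The opening summary and Background and Rationale both define the waitlist condition as the untreated period, which points to the second baseline and rules out readings after crossover. That stands as far as intent goes, and it makes a treated-versus-treated analysis an unlikely choice. It does not rescue the 1-month claim: the second baseline is still about 4 weeks short of Time 3, and the assumption of no natural change is not stated.

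A second reply is that this is a feasibility pilot and only the 1-month clause of its secondary hypotheses is touched. That also stands and limits the weight of the point.

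Some stronger readings are tempting but are not supported:

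- *The 1-month contrast is always the worse matched of the two.* Only the signed gap is always 4 weeks larger. If the second baseline slipped beyond week 10 + d, Time 3 would be the better matched.
- *The bias favours the interventions.* The documents fix neither the drift nor the sign of the gap.
- *Planning versus Engagement at 1 month is missing from the hypotheses.* H0-1 and H0-2 cover all groups at both time points. What is absent is a directional alternative, although Background and Rationale raises the possibility that conventional BA "would lead to more generalised and lasting gains than simply engaging in rewarding activities without such knowledge and skill acquisition" and sets out to learn "whether one or other intervention is superior in improving mood and activity levels".
- *Re-randomised waitlist participants must be left out of the 1-month comparison.* The Randomisation Procedure gives them their own pre-generated, blocked sequence, opened after the second baseline. Planning versus Engagement is therefore randomised among them too.

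The flow chart is not shown in the text reviewed, but the written schedule is consistent throughout and leaves little room for another visit.

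**Conclusion.** The point holds for the 1-month Waitlist comparison in all four hypotheses, and for nothing wider. No untreated waitlist reading is scheduled to match the active arms' 1-month follow-up. The available substitutes are about 12 weeks of change against about 8, or treated against treated.

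That conclusion rests on the written schedule and needs no assumption about drift. The range of -0.12 to +0.12 SD illustrates what an assumed drift would do and is not an estimate.

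The pre-to-post contrast has an untreated control, which is time-matched provided Time 2 and the second baseline fall at similar intervals from first baseline. That proviso deserves checking, because the section on assessment and management of risk treats delay before groups begin as inevitable. The randomised Planning versus Engagement comparison and the feasibility objective are unaffected by this gap. The consequence is modest, but the hypotheses as worded claim something the design cannot deliver cleanly, and the correction is nearly free.

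**What to change.** In HA-1, HA-2, H0-1 and H0-2, limit the Waitlist comparison to pre-to-post: Time 1 to Time 2 in the active arms against first to second baseline in the waitlist arm. The null hypotheses can keep the 1-month time point for Planning versus Engagement.

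In the Analysis section, state that:

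1. the second baseline is the waitlist control value, and no reading after crossover is ever coded as Waitlist;
2. at 1 month, the reported comparisons are the randomised Planning versus Engagement contrast and within-arm maintenance;
3. re-randomised waitlist participants may enter the 1-month contrast by re-randomised arm, with stratification by initial allocation;
4. weeks from first baseline to each assessment are reported by arm.

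Item 3 is worth having. With n per initial arm, about 1:1 re-randomisation, equal variances and no drop-out, leaving these people out would raise the standard error of the 1-month contrast by a factor of sqrt(2/n) / sqrt(2/(1.5n)) = sqrt(1.5) = 1.22, or about 22%.

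The cost is the wording of four hypotheses and about four sentences of analysis text. No visit, wait or group start changes. The downside is that the claim of a 1-month effect versus waitlist is dropped.
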